13. DATA MANAGEMENT

Data will be collected from three main sources: 1) data collected by trial staff on trial case report forms for later entry into the data management system (DMS); 2) data generated by ancillary facilities, such as Quest laboratories, and sent to the research clinic; and 3) data derived from ESHA software, estimating the nutrient content of the intervention. The DMS will be accessible only via the secure website and only to authorized personnel. Data entered into the DMS will be subject to intra- and inter-item checks, such as range checks, logic checks, and consistency checks. Missing data items will be noted in the database, although certain key values (e.g. uric acid) will not be allowed to be marked 'missing.' Data entry staff will perform data entry as soon as possible after data have been collected.

Data confidentiality and integrity

The investigative team, including staff at all levels of the study will be trained on the importance of data integrity and maintaining participant confidentiality, including HIPAA (Health Insurance Portability and Accountability Act). All data will be stored on secure servers. All study-related computers will be located behind appropriate firewalls and will maintain automated virus update mechanisms. Printed materials will be maintained in locked rooms and file cabinets. All staff will sign statements attesting to their understanding of and willingness to abide by policies regarding confidentiality and data integrity.

Trial-wide data release.

De-identified trial data will be shared with external investigators on an individual basis through contact with the trials' principal investigator.

14. TIMELINE

The trial consists of three main phases: planning and protocol development, implementation (recruitment, intervention and data collection), and data analysis/dissemination. Protocol and intervention development will start in Year 1. Recruitment, randomization, and follow-up will commence in Year 1 and last approximately 15 months, allowing us to meet our recruitment target of 1-2 patients per month. The remaining time will be devoted to data analyses, presentation/publication of findings, and other dissemination activities.

Project Years	1				2			
Calendar Year	7/2017 - 6/2018				7/2018- 6/2019			
Quarters	1	2	3	4	1	2	3	4
Protocol Development								
Intervention Development								
Recruitment, Randomization, Follow-up								
Data Analysis and Publication								

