1. ABSTRACT

The conceptual framework of the proposed trial is grounded in our prior experience in the conduct of dietitian-directed dietary interventions with the provisions of food. In this randomized controlled trial (RCT), the Diet-Gout trial or DIGO, we will randomize at least 40 adults with gout and with hyperuricemia (serum uric acid [SUA] ≥ 7 mg/dL) who are not actively taking urate-lowering drugs (ULDs) to a grocery intervention designed to reflect the previously published Dietary Approaches to Stop Hypertension (DASH) diet. This trial has been funded by the Rheumatology Research Foundation. Following a crossover design, all 40 adults will undergo 4 weeks of a self-directed feeding period (reference) and a DASH grocery intervention (value \$105 per week). The primary outcome is serum uric acid. Our approach is adapted from the framework of the recently completed “Five Plus Nuts and Beans Trial.” Groceries will be purchased from an online grocery store (AmazonFresh) in serving proportions that reflect the DASH diet – a diet high in fruits, vegetables, low-fat dairy and lean meats and low in fat and saturated fat. This, as a corollary, will reduce consumption of a pro-gout dietary pattern: an unhealthy dietary consumption pattern that is due in parts to excesses (e.g., red meat and sugary soda) and deficiencies (e.g., vegetable protein and low-fat dairy) in typical American diets.

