6. RECRUITMENT

Field centers

The trial will be conducted at a well-established field center in Central Maryland, namely, the ProHealth clinical research unit in West Baltimore, Maryland.

The ProHealth Clinical Research Unit is a dedicated research facility that has been the site for numerous NIH-sponsored trials. This participant-friendly clinical research facility is 15,000 ft² located in the Woodlawn suburb of Baltimore and is convenient to participants from Baltimore City, Baltimore County, Anne Arundel County, and Howard County. ProHealth has 9 exam rooms and 2 phlebotomy stations and space for up to 50 staff.

Recruitment strategies

We will implement a variety of strategies to achieve our recruitment target, i.e. ~40 participants. Our experience is that multiple strategies work synergistically to promote study name-brand recognition to enhance recruitment. We will employ the following approaches:

- (1) EPIC patient portal messages to patients of Johns Hopkins Hospital with an active patient portal. The Johns Hopkins University Core for Clinical Research Data Acquisition will develop a dynamic query of Hopkins patient's with a gout ICD-9 or ICD-10 code, age>18 years, and in zip codes surrounding the ProHealth Clinical Research Center. Those with an active patient portal will receive a portal message with a link to our website and other contact information. Those with an inactive patient portal will receive a mail invitational letter.
- (2) Community-based recruitment will be performed using a mailed brochure with a stamped, self-addressed reply card. Addresses will be purchased from local vendors.
- (3) Periodical advertisements: We will place a banner ad in local newspapers surrounding our clinical research center.
- (4) Billboards, radio, and bus advertisements will be considered targeting our immediate geography.
- (5) Facebook advertisements (including Instagram): These will target users with an interest in gout in the region surrounding our clinical research center. Advertisements will direct interested adults to our trial website.
- (6) Clinic contact: Study brochures will be placed in the rheumatology clinic waiting areas.

Recruitment of women and minorities

Given the demographic characteristics of individuals residing in central Maryland with gout, we anticipate that ~80% of participants will be men and ~40% will be African-American.

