10. INTERVENTIONS

Distribution and adherence

Overview: The intervention groups are summarized below. Participants will complete each of the study periods in random order. Participants will be asked not to start diuretics or ULD during the trial period (i.e., 10-12 weeks from SV1 to FP2).

Self-Directed (SD): The SD group was asked to continue their typical routine for grocery shopping and meal preparation.

Dietitian-Directed Tailored DASH diet (DD) Group: The DD intervention will consist of a one-on-one session with a dietitian at baseline, followed by weekly calls and assistance with food purchases. After the initial one hour visit, the dietitian will meet with the participant by phone every week to order next week's groceries. Participants will be allotted a stipend of \$105/week for the purchase of food (i.e. \$15/day). We will work with AmazonFresh to order and deliver foods to the ProHealth research center for weekly pick-up. Food will be ordered in fixed proportions reflecting the DASH diet:⁶ 4 servings/day of fruit, 3-4 servings/day of vegetables, 1-2 servings/day of lean meat (poultry/fish), 1-2 servings/day of low fat dairy, and 1-2 servings/day of high fiber foods (nuts, beans). During the intervention period participants will be asked to restrict alcohol, sugary beverages (no soda, no juice), red meat, shellfish, organ meats, and sweets. Food orders will be selected to be low fat, low saturated fat, and low cholesterol with a sodium target of <2300 mg per day. Little education will be provided during the DASH grocery intervention to minimize carryover effects. Rather, education will be focused on how to consume diet per the trial protocol.

Orders will target the following weekly servings with an emphasis on fruit/vegetables/dairy if budget constraints:

- i. Grain: 36-49 servings (5-7/d)
- ii. Vegetables: 28 servings (4/d)
- iii. Fruit: 28 servings (4/d)
- iv. Low fat/fat free dairy: 14 servings (2/d)
- v. Lean animal protein: 9-14 servings (1-2/d)
- vi. Nuts/Seeds/Legumes: 2 servings (<0.5/d)
- vii. Fats/oils/spices: not applicable; use over week

Monitoring Adherence

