12. ANALYSIS

The trial has sufficient resources to enroll 40 participants who will be randomly allocated to 1 of 2 sequences for each the two groups: (1) the SD group followed by the DD group or (2) the DD group followed by the SD group.

Power and sample size

Based on a cross-over trial design, using a variance of 1.71 at an alpha level of 0.05 with a power of 0.8, we estimated that we would need 41 participants to detect a change of -0.75 mg/dL between interventions.¹³ In two prior studies we had observed reductions of -1.3 and -1 mg/dL among subpopulations with a uric acid above 7 mg/dL.^{5,14}

Analysis Plan

This study is a randomized trial that tests the effects of an innovative intervention against a minimal intervention on a selected set of outcomes. The analysis will be conducted under the intent-to-treat principle for both the primary and the secondary endpoints. For the Primary Aim, groups will be compared using within-person differences in SUA levels. The analysis will be carried out with generalized estimating equations to compare 4-week SUA levels from both phases of the study, adjusted for baseline. This will allow us to test the null hypothesis that there is no difference in uric acid between the DASH diet intervention and the self-directed group (reference). Other outcome variables will be analyzed with a similar approach. For continuous outcomes, the distribution of outcome residuals will be assessed for normality and transformed where appropriate. Continuous outcomes will be analyzed via an identity function, while binary variables will be evaluated via a logit function.

Missing data

Based on the existing literature, we will employ recommended strategies to address missing data.⁷¹⁻⁷⁴ However, every effort will be made to collect outcome data on all participants.

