3.2 Power and sample size

Based on a cross-over trial design, using a variance of 1.71 at an alpha level of 0.05 using a twosided paired means test with a power of 0.8, we estimated that we would need 41 participants to detect a 4-week difference of -0.75 mg/dL between interventions.² In two prior studies we had observed reductions of -1.3 and -1 mg/dL among subpopulations with a uric acid above 7 mg/dL.^{3,4}

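### The protocol's timeline implies 15-30 participants at its stated monthly rate, not the roughly 40 planned or the 41 said to be needed

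*Protocol*

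**What the plan says.** Protocol Section 14 describes one block of activity: "Recruitment, randomization, and follow-up will commence in Year 1". It says this block will "last approximately 15 months, allowing us to meet our recruitment target of 1-2 patients per month". The accompanying table spans two project years, 7/2017 to 6/2019.

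The planned size appears in several places:

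- Protocol Section 1: "we will randomize at least 40 adults with gout".
- Protocol Section 4 also gives 40.
- Protocol Section 6: "our recruitment target, i.e. ~40 participants".
- Protocol Section 12: "The trial has sufficient resources to enroll 40 participants". The power paragraph of the same section then says "we estimated that we would need 41 participants to detect a change of -0.75 mg/dL between interventions".
- SAP 3.2 repeats the requirement: "we would need 41 participants to detect a 4-week difference of -0.75 mg/dL between interventions".

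Protocol Section 10 gives each participant's time in the trial as "10-12 weeks from SV1 to FP2".

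**The concern.** The protocol uses the term recruitment target for two quantities that cannot both hold: a total of about 40 in Section 6, and a monthly rate in Section 14 that yields at most 30 in the time allowed. Even the upper end of the rate is 10 short of 40 and 11 short of 41. The 15 months also have to contain follow-up, so the plain product is generous.

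The rate and duration are the only figures by which a reader can judge whether the planned size is achievable. If they are right, the planned size is not reached in the stated time. If the planned size is right, the rate or the duration is misstated. Power is affected too, because the sample-size statement assumes 41.

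**Working it through.** **Inputs.** Rate 1-2 per month and about 15 months including follow-up (protocol Section 14). SV1 to FP2 10-12 weeks (Section 10). Planned size 40 (Sections 1, 4, 6, 12). Required size 41, difference 0.75 mg/dL, variance stated as 1.71, alpha 0.05, power 0.8 (Section 12 and SAP 3.2). Two-sided paired means test (SAP 3.2).

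**Step 1: reproduce the plan's 41.** For paired means, n = (z₀.₉₇₅ + z₀.₈₀)² × Var(difference) / δ², with (1.960 + 0.842)² = 7.849 and δ² = 0.5625.

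- 1.71 as the SD of the within-person difference: 7.849 × 2.924 / 0.5625 = 40.8, so 41. This reproduces the plan's figure (43 by noncentral t).
- 1.71 as the variance of the difference, as labelled: 7.849 × 1.71 / 0.5625 = 23.9, so 24 (26 by t). Not reproduced.
- 1.71 as a per-period within-person variance, so that the difference has variance 3.42: 47.7, so 48 (50 by t). Not reproduced.

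**Step 2: accrual at the stated rate.** 15 × 1 = 15 and 15 × 2 = 30. The shortfall is 10-25 against 40 and 11-26 against 41.

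**Step 3: allow for follow-up inside the window.** Ten weeks is 70 / 30.44 = 2.30 months and twelve weeks is 84 / 30.44 = 2.76 months. If the last FP2 must fall within 15 months, entry at SV1 is open for 15 − 2.30 = 12.70 down to 15 − 2.76 = 12.24 months. At 1-2 per month that is about 12-25 participants.

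**Step 4: what 40 would require.**

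- Rate over the full 15 months: 40 / 15 = 2.67 per month (41 / 15 = 2.73).
- Rate with follow-up inside the window: 40 / 12.70 = 3.15 to 40 / 12.24 = 3.27 per month.
- Duration at 2 per month: 40 / 2 = 20 months of entry. At 1 per month it would be 40 months, longer than the 24-month project table.

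**Step 5: power for 0.75 mg/dL, two-sided 0.05.** Normal approximation: Φ(0.75√n / SD − 1.96). For example, at n = 40 and SD 1.71: 0.75 × 6.325 / 1.71 − 1.96 = 0.814, giving 79%. The t columns use the noncentral t with n − 1 degrees of freedom.

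| n | SD 1.71, normal | SD 1.71, t | Variance 1.71, normal | Variance 1.71, t |
|---|---|---|---|---|
| 15 | 40% | 35% | 60% | 54% |
| 25 | 59% | 56% | 82% | 79% |
| 30 | 67% | 64% | 88% | 86% |
| 40 | 79% | 77% | 95% | 94% |
| 41 | 80% | 78% | 96% | 95% |

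On the per-period variance reading, power by t is 31% at 15, 57% at 30 and 71% at 40.

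The bars of the Section 14 chart were not available in the text reviewed and play no part in this check.

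**The case against.** The multiplication cannot be disputed, but four arguments limit what follows from it.

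*Power is not lost on every reading.* A reader might infer that the timeline forfeits 80% power outright. The documents call 1.71 a variance. If it is the variance of the within-person difference, 26 participants suffice by the t-test and 30 give 86%. Power fails across the whole 15-30 range only if 1.71 is an SD or a per-period variance. This objection stands, so any statement about power has to be conditional.

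*Nothing says enrolment would stop short.* A reader might infer that the team would meet its monthly target, appear on schedule and finish with too few. Protocol Section 8 does commit to tracking observed against expected enrolment, but it does not define the expected figure as 1-2 per month. Section 6 sets the target as a total, and no section closes enrolment at 15 months, which is itself approximate. Recruitment might simply run longer: 20 months at 2 per month fits inside the 24-month table, though it leaves little room for set-up, the last participants' follow-up and analysis. This also stands.

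*40 against 41 is immaterial.* By either method the difference is about one point of power. Comparing the plan's 80% with a t-based 77% at n = 40 would mix methods, since the t-test gives only 78% at 41. The gap that matters is 15-30 against 40.

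*The practical effect is small.* The SAP is dated May 20, 2019 and the project table ends in 6/2019, so most of the planned recruitment period had probably passed. The sentence does not touch the estimand, randomization, analysis or safety. This lowers the priority but does not make the figures agree.

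The lack of a stated drop-out allowance is a separate matter. Any loss figure would be an assumption, and the planned estimating-equations analysis (SAP 3.1) can use a participant who has only one period. It is not needed for this point.

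**Conclusion.** The inconsistency is real. Section 14's rate and duration give 15-30 participants, or about 12-25 with follow-up inside the window, against about 40 planned and 41 stated as necessary. This rests only on the protocol's own figures. The lower range also assumes that entry is counted at SV1 and that the last FP2 must fall within 15 months.

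The consequence for power is conditional. At the top of the stated rate (n = 30), power for 0.75 mg/dL by t is 64% if 1.71 is the SD of the difference, the only one of the three readings in Step 1 that reproduces 41. It is 86% if 1.71 is the variance of the difference. At the 40 planned, the corresponding figures are 77% (79% by the normal approximation) and 94%.

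This is a minor to moderate fault in the plan's feasibility figures. It does not show that the trial under-enrolled or would have stopped early, because the documents contain no enrolment results and no rule ending recruitment at 15 months.

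**What to change.** In protocol Section 14, do one of the following:

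- restate the monthly target as at least about 2.7 per month, or about 3.1-3.3 if FP2 must fall within the 15 months;
- lengthen the stated recruitment period (20 months of entry at 2 per month) and say whether follow-up comes on top;
- keep 1-2 per month and state the size and power it gives.

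In protocol Section 12 and SAP 3.2, say whether 1.71 is the SD or the variance of the within-person difference, or a per-period variance. Then state power for the 40 planned on that basis: about 79% by the normal approximation or 77% by t if it is the SD of the difference, and about 94% by t if it is the variance of the difference.

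The cost is wording only. No extra enrolment, procedure or change of analysis is asked for. The stated timeline becomes more demanding or longer, and on the SD reading the stated power falls slightly below 80%.

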**Dietary Approaches to Stop Hypertension
(DASH) Diet effects on Serum Uric Acid
(SUA) in adults with hyperuricemia and
gout.**

DIGO

THE DIET GOUT TRIAL

STATISTICAL ANALYSIS PLAN

VERSION 1.0

May 20, 2019

NCT03569020

Table of Contents

1	Introduction	3
	Primary aim	3
	Other aims	3
2	Data Source	4
3	Primary Outcome: Serum Uric Acid	5
	Randomization and primary analysis	5
	Power and sample size	5
	Pre-specified Stratified Analysis	5
	Sensitivity analyses	6
4	Other outcomes	7
	Analysis	7
5	Missing data	9
6	Safety outcomes	10
7	References	11

1 Introduction

DIGO is an individual level, crossover, randomized trial to determine the effect of 4-weeks of DASH groceries' on serum uric acid in 40 adults with self-reported gout and hyperuricemia and not on urate lowering therapy. Participants are randomly assigned to 1 of 2 sequences: (1) the DASH grocery intervention followed by the self-directed diet or (2) the self-directed diet followed by DASH groceries.

The **primary outcome** is the difference in mean uric acid measured in serum after each feeding period.

1.1 Primary aim

To determine the effect of the DASH Diet on serum uric acid among adults with self-reported gout and hyperuricemia. In this crossover, randomized controlled trial (RCT) of 40 patients with hyperuricemia (SUA level $\geq 7\text{mg/dL}$), we will compare a DASH diet grocery intervention vs. a self-directed control diet over 4 weeks to determine the effect of the DASH diet on uric acid.

1.2 Other aims

To estimate the effects of the DASH diet on the following outcomes:

- A. Clinic blood pressure
- B. Orthostatic hypotension
- C. Timed Up and Go
- D. Body mass index
- E. Urinary sodium, potassium, and creatinine excretion
- F. Self-reported fruit, vegetable, and fat consumption
- G. Gout severity and flares
- H. Global physical function
- I. Joint pain
- J. Fasted LDL cholesterol
- K. Fasting blood sugar
- L. Urine pH and uric acid level

2 Data Source

Data will be entered by clinic staff into a REDCap dataset. Grocery nutrient information will be derived from the ESHA platform. Backup files of the database will be generated and stored at regular intervals in a secure, off-site location, to permit regeneration of the database in the event that it is destroyed.

3 Primary Outcome: Serum Uric Acid

3.1 Randomization and primary analysis

Participants will be randomized using a computer-generated randomization scheme with varying sized blocks to 1 of 2 sequences in a 1:1 ratio such that approximately half of participants will undergo the DASH grocery intervention first followed by the self-directed phase while the other half will undergo the self-directed (reference) phase first, followed by the DASH grocery intervention. There is no washout period.

We will first confirm that the residuals of uric acid are normally distributed (if not these values will be log-transformed). We will then assess for carryover effects by: (1) examining a period variable in relation to uric acid (temporal effects) and (2) an intervention-by-period interaction term. If this is significant, we will conduct a period 1 only analysis (treating the trial as a parallel design), comparing the unpaired effects of 4-week DASH groceries on uric acid compared to 4 weeks of the self-directed group. This will be performed with linear regression adjusted for baseline uric acid values.

If there is not sufficient evidence of a carryover effect, we will compare serum uric acid measurements from both periods within person using the trial's crossover design. These comparisons will be performed with generalized estimated equations (normal distribution, identity function) with an exchangeable working matrix and robust variance estimator. These analyses will be adjusted for baseline uric acid measurements.¹

We will use an intent-to-treat approach for either of the two scenarios above.

Our hypothesis is that 4-weeks of the DASH grocery intervention will lower serum uric acid compared to 4-weeks of the self-directed diet. The null hypothesis is that there will be no difference in uric acid between either phases of the study.

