3.4 Sensitivity analyses

1. Models will be run with no adjustment for baseline uric acid
2. We will perform an on-treatment analysis: (i) persons who ate 25% or less of non-study foods during the DASH grocery intervention, (ii) persons whose estimated Calorie intake was met or exceeded by the food provided through the DASH grocery intervention, and (iii) persons who did not change antihypertensive medications or urate lowering therapies during the post-randomization study period
3. We will perform an analysis excluding women
4. Depending on whether there were carryover effects, we will perform the parallel (period 1 only) or crossover analysis as a sensitivity analysis.

4 Other outcomes

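### A carryover pre-test chooses the primary analysis, which raises the type I error and can replace the powered crossover with an unpowered 20-versus-20 comparison

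*SAP*

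**What the plan says.** SAP 3.1 (Randomization and primary analysis) allocates participants "to 1 of 2 sequences in a 1:1 ratio" with no washout. Carryover is then assessed by "examining a period variable in relation to uric acid (temporal effects) and (2) an intervention-by-period interaction term". The consequence follows: "If this is significant, we will conduct a period 1 only analysis (treating the trial as a parallel design"), fitted by linear regression on period 1 with baseline uric acid as covariate. If carryover is not shown, the primary analysis is a baseline-adjusted GEE on both periods.

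The SAP does not state the level of the pre-test. It does not say whether the switch depends on the interaction alone or also on the period variable. It makes no allowance for the pre-test in alpha or power.

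SAP 3.4 (Sensitivity analyses), item 4, gives the analysis that was not chosen a secondary role: "we will perform the parallel (period 1 only) or crossover analysis as a sensitivity analysis". SAP 3.2 powers only a paired comparison. Protocol section 12 names only the two-period GEE, so the pre-test and the fallback exist only in the SAP.

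**The concern.** The outcome data decide which analysis is primary, and the deciding test is not independent of the test that follows. In this design the intervention-by-period interaction is the same contrast as the difference between sequences in a person's total over both periods. Half of that total is the period-1 value, which is all the fallback uses. The fallback is therefore run mainly in trials where the period-1 groups already differ by chance, and its p-value no longer has a 5% level.

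A second problem is the period variable. A period effect is a time trend common to both sequences. It is not carryover, and a model term removes it. If it counts as a trigger, a harmless trend discards half the data.

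At stake are the level of the primary test and, whenever the switch occurs, a primary comparison of 20 against 20 that the sample size was never meant to support.

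**Working it through.** **Inputs.** SAP 3.2 works from "using a variance of 1.71 at an alpha level of 0.05 using a twosided paired means test with a power of 0.8" to "detect a 4-week difference of -0.75 mg/dL between interventions", and reports: "we estimated that we would need 41 participants". Protocol section 12 says: "The trial has sufficient resources to enroll 40 participants", which gives 20 per sequence. Three inputs are not in the documents and are assumed: the between-person spread (SD 0.7-1.3 mg/dL, or a correlation ρ of 0.3-0.9 between a person's measurements), the pre-test level (0.05 and 0.10), and no dropout.

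**1. The plan's own figure.** For a paired test, n = V × (1.960 + 0.842)² / 0.75² = V × 7.849 / 0.5625, where V is the variance of the within-person difference.
- V = 1.71: n = 23.9, so 24.
- V = 1.71² = 2.924: n = 40.8, so 41.
- V = 2 × 1.71 = 3.42: n = 47.7, so 48.

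Of these readings, only an SD of 1.71 for the difference gives 41. Both the SD reading (1.71) and the literal variance reading (SD √1.71 = 1.31) are carried forward. With N = 40, crossover power by noncentral t is 77% and 94% respectively.

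**2. Why the two tests are linked.** Let Y1 and Y2 be a person's two end-of-period values. The pre-test compares Y1 + Y2 between sequences and the fallback compares Y1. After baseline adjustment the correlation of Y1 with Y2 is ρ/(1 + ρ), so the correlation of the two contrasts is √[(1 + 2ρ) / (2(1 + ρ))].
- ρ = 0.3: √(1.6/2.6) = 0.78.
- ρ = 0.9: √(2.8/3.8) = 0.86.

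The crossover test uses Y1 − Y2, which is uncorrelated with Y1 + Y2, so that branch keeps its 5% level.

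**3. Type I error.** Overall error = (1 − a) × 0.05 + a × c, where a is the pre-test level and c is the rejection rate in null trials sent to the fallback. Simulation (20 per sequence, no effect, no carryover, paired t for the crossover, baseline-adjusted regression for the fallback) gives c.
- Baseline-adjusted pre-test, a = 0.05, ρ 0.3-0.9: c = 41-51%. By the formula, 0.0475 + 0.05 × 0.41 = 6.8% and 0.0475 + 0.05 × 0.51 = 7.3%. Direct simulation gives 6.9-7.3%.
- Same, a = 0.10: c = 30-35%. By the formula, 0.045 + 0.10 × 0.30 = 7.5% and 0.045 + 0.10 × 0.35 = 8.0%.
- Between-person SD 0.7-1.3, pre-test with or without baseline adjustment: c falls as low as 22% without adjustment. Overall error is 5.8-7.3% at 0.05 and 6.2-8.1% at 0.10.
- Crossover fixed in advance: 4.9-5.1%.

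**4. Power of the fallback taken alone.** The residual variance is (V/2)(1 + ρ), and the standard error is √(2 × residual variance / 20). Example, SD reading, ρ = 0.5: 1.462 × 1.5 = 2.193; SE = √0.2193 = 0.468; 0.75/0.468 = 1.60; power about Φ(1.60 − 1.96) = 36%, or 35% by t.

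| ρ | SD reading (crossover 77%) | Variance reading (crossover 94%) |
|---|---|---|
| 0.3 | 39% | 59% |
| 0.5 | 35% | 53% |
| 0.7 | 31% | 48% |
| 0.9 | 28% | 44% |

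Reaching 80% would take about 54-78 per arm (SD reading) or 32-46 per arm (variance reading).

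**5. Does the pre-test protect?** A real carryover of 0.5 mg/dL is flagged at 0.05 in about 8-14% of simulated trials.

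**6. If the period variable is also a trigger.** An assumed 0.5 mg/dL period effect sends about 39-67% of trials to the fallback, depending on how the period test is built. Overall power for 0.75 mg/dL drops from 77% to about 58-62%, or from 94% to about 66-73%.

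**The case against.** The strongest reply is that the overall damage is moderate. Without carryover, the interaction sends only about 1 trial in 20 to the fallback. Type I error is then 1-2 points high at a 0.05 pre-test, and power of the whole procedure falls by only about 1-5 points across pre-test levels of 0.05 and 0.10. That stands: the halving of power describes the period-1 analysis alone, not the procedure on average.

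The wording also favours the interaction as the trigger, because the alternative branch speaks of evidence of carryover. The period-trigger losses are therefore conditional on the other reading and on an assumed period effect. The ambiguity remains, since the period variable is listed as part of the carryover assessment.

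With no washout, carryover is a fair worry, and fixing the crossover does not remove it. The crossover estimate loses half the carryover: with 0.5 mg/dL, a true 0.75 is estimated as 0.75 − 0.25 = 0.50, and power is about 43% (SD reading) or 64% (variance reading). The SAP's rule rejects slightly more often there, but partly through a test selected on the same data. A check that misses most real carryover is not a remedy.

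Finally, SAP 3.4 item 4 ensures that both analyses are reported. This helps transparency, but the data still choose which one is primary.

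**Conclusion.** The concern holds. As written, the primary test does not have its stated 5% level: about 5.8-7.3% with a 0.05 pre-test and 6.2-8.1% with 0.10. No real carryover is needed for this inflation. A null trial that reaches the fallback at a 0.05 pre-test rejects 22-51% of the time. The fallback taken alone has roughly 0.4-0.6 of the crossover's power, and the pre-test seldom detects the carryover it is meant to find.

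The exact figures depend on the assumed between-person variation, the unstated pre-test level, whether the pre-test is baseline-adjusted, the reading of 1.71, and 40 completers. The direction does not depend on these, because it follows from the shared period-1 data. The rule also departs from protocol section 12 and from the analysis that SAP 3.2 powers. It must be fixed because it determines the primary p-value.

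**What to change.** In SAP 3.1, delete the conditional rule. Make the two-period, within-person analysis with a period term the primary analysis, whatever the carryover assessment shows. Report the sequence contrast with its confidence interval as description only, with no decision attached. In SAP 3.4 (Sensitivity analyses), replace item 4 with a commitment always to report the period-1 baseline-adjusted regression as a sensitivity analysis.

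This brings the SAP back into line with protocol section 12 and with the paired comparison it powers. It costs a few lines of wording and no new data. The downside is that any real carryover pulls the crossover estimate toward no effect by half its size. The period-1 analysis can indicate this, but at 20 per arm only imprecisely, and the report should say so.
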